**Attachment Name Category Version Date Attached**

211 Quitline Phone

Recruitment:Screening Script.rtf Recruitment Script: [contact]

211 Phone Consent Script for

Collateral Contacts.rtf Recruitment Script: [contact]

**1.8.a** List the individual data elements you will need to access/use from the patient or clinic records to identify potential participants for recruitment

Patient health records will not be accessed. For the interview/questionnaire we are collecting personal, identifiable information i.e name, DOB, and mailing address to receive compensation, insurance status, any existing health conditions as a result of smoking, existing mental health conditions, etc. Please see attachments "Baseline Survey"

**1.8.b** What is the plan for participant identifiers obtained to identify participants for recruitment?

Identifiers for both those who enroll and those who do not enroll will be retained beyond the period of recruitment and enrollment of participants

• Data analysis/verification

**1.8.c** Does the research team agree that the requested information will not be reused or disclosed to any other person or entity, except as required by law, for authorized oversight of the study, or for other research for which the use or disclosure of the requested information would be permitted by the HIPAA Privacy Rule?

Yes

**1.9** Will you use a screening log or other record that would include information on people who do not consent to participate in the study?

No

**1.10** Describe where the consent discussion will occur (check all that apply):

• Private room or area

• By phone

**1.11** Participants and/or their legally authorized representative will have (check all that apply to the consent process and explain process in Question 1.12 below):

• As much time as they desire to consider enrolling in the study, including:

An opportunity to thoroughly review the consent materials with knowledgeable members of the research team, and with family and/or friends as appropriate

Sufficient time to have all of their questions answered

**1.12** Provide a description of the enrollment and consent process in sequential order and address EACH of the bulleted points below:

Describe each study population separately including control population

Describe when recruitment and consent materials are used

Indicate how much time individuals will have to consider participation

Use THIRD person active voice. For example, "the principal investigator will identify potential participants, the study coordinator will discuss the study with participants over the telephone and schedule the first study visit, etc..."

Describe the steps that will be taken by the research team to minimize the possibility of coercion or undue influence during the consent process

The study population will come from United Way 2-1-1 callers that are Missouri residents who are 18 years and older, have self-identified as smokers. United Way 2-1-1 is not engaged in research activity. United Way 2-1-1 Missouri Information Specialists will identify callers that are English-speaking, not experiencing crisis, 18 years and older, and are cognitively capable of understanding the process and what is being asked. Once callers have been screened by the 2-1-1 Information Specialists using the provided recruitment telephone script, express interest in the study, they will be considered to be interested and potential study participants by 2-1-1. Their contact information will be recorded in a spreadsheet and electronically retrieved by the Washington University (WUSTL) Research team at the close of the recruitment period (end of the business day Monday-Friday over the three year recruitment period). United Way 2-1-1 will NOT do any consenting. They will only invite callers to participate in the research project. When the spreadsheet is received, the participants' information will be entered into a secure database. After which, participants will be contacted by the WUSTL research staff to confirm their interest and eligibility, obtain verbal informed consent, administer the baseline survey, and obtain detailed contact information and preferences. This process will happen in 1-2 business days after the information has been received from United Way 2-1-1. After completing the baseline assessment, participants will be enrolled into quitline services, and wait to be contacted by the quitline (Alere Wellbeing, Inc./Optum) in the next 1-3 business days. During this time, collateral contacts will also be consented to be called during the study if the participants cannot be reached on their primary and secondary numbers provided.

For participants completing the urine test, verbal consent will be obtained over the phone, prior to mailing the testing kit. Participants will be contacted within 1-2 business days of completing the 6-month follow-up survey to consent to the urine test and review instructions. The urine test will be offered to all participants who reported smoking abstinence at 6-month follow-up.

Re-consenting of participants regarding the audio recordings will take place by telephone and documented in their study record. This language has been modified in the updated consent document that has been uploaded.

**1.13** Provide a detailed description in sequential order of the study procedures following the consent process - DO NOT cut and paste from the Consent Document.

Describe study populations separately if they will be participating in different procedures

DESCRIBE:

Control populations, if applicable

Any randomization, if applicable

What participants will be asked to do/what happens in the study (in sequential order)

The time period over which procedures will occur

Long-term follow-up and how it occurs

The recruitment and study procedures will occur for about 3 years. Participants will be asked to participate in the study for a total of six months that will include completing the quitline coaching sessions which can take 1-4 months, and follow-up at 3 and 6 months; however, they can withdraw from the study at any time. During this time, half of the participants will also be asked to work with a Navigator to assist with the basic needs from their initial 2-1-1 call.

The control population will only receive the Standard Quitline (standard of care): Alere's Quit for Life program helps smokers set a quit date within 30 days of enrollment and provides one coaching call before and four carefully timed calls after the quit date to prevent relapse. Calls are scheduled at the smoker's convenience, can be spread over 1-3 months around the quit date, and are adjusted based on the individual's quit success or other needs. Quit coaches try up to five times to reach a smoker for each counseling session. The counseling goal is to increase a smoker's readiness to quit and develop an individually tailored quit plan. In Missouri, Alere provides: (1) up to four sessions of proactive cognitive behavioral counseling by phone from trained quit coaches; (2) access to the same quit coach each call (3) unlimited calls to a toll-free phone number by the smoker and access to Alere's WebCoach® online service and live chat; (4) self help print materials (i.e., "Quit Guide"); (5) tailored motivational emails and/or personal interactive text messages sent throughout the quitting process; and (6) up to 2 weeks of free NRT (patch or gum) for eligible smokers. The quitline also can provide materials for family members to help them support the smoker's quit attempt.

One treatment group will only receive the Specialized Quitline: Very low-income smokers are different from other smokers in important ways not always addressed by standard quitline services. As summarized in Table 2, these differences dictate modifications to counseling protocols, content and personnel. The research team and Alere staff will create and pre-test custom protocols, scripts, prompts and other content to maximize intervention relevance and acceptability to very low-income smokers. RIU coaches who will be delivering the Specialized Quitline services will receive training from clinical quitline staff, the research team and 2-1-1 staff who have extensive experience with the target population. Focus areas for training and distinctive content and protocol for the Specialized Quitline include:

- Health Literacy
- Abstract vs. concrete language
- Lived experience
- Resource constraints.
- Future orientation.
- Getting cigarettes.

- Living situation
- Phone/online access.

The remaining two treatment groups will receive either the Standard or Specialized Quitlines with a Navigator. Navigators will: (1) identify and assess smokers' needs, including the reasons they called 2-1-1; (2) jointly generate solutions to address the needs; (3) develop plans to carry out the solutions, including; (4) help prioritize among multiple needs; (5) identify community resources that could help solve the problem; (6) determine eligibility for services; (7) help smokers access available resources by scheduling appointments and provide appointment reminders; (8) prepare smokers to interact with service agencies and/or act as an advocate on their behalf; (9) provide instrumental support such as arranging transportation; (10) actively intervene to resolve barriers to basic needs solutions; (11) oversee follow-up of problem solving actions; and (12) review progress made towards resolving unmet basic needs and adapt solutions accordingly.

Follow-up: Follow-up at 3 & 6 months. The primary study outcomes are cessation-related. Participants will be asked if they smoked at all in the past 7 days and past 30 days to assess point prevalence abstinence. Those who report any smoking in the past 7 days will be asked if they quit for at least 24 hours since the previous survey and to report on their nicotine dependence measured by the Heaviness of Smoking Index (cigarettes per day; time elapsed between waking and smoking). These items from the Fagerstrom Test of Nicotine Dependence are reliable over time with good predictive validity. All participants will report use of any pharmacologic cessation aids (i.e., NRT, bupropion, Chantix), self-help, or counseling resources they have used since the prior survey. Successful quitters ( 7 days) will report their confidence in staying quit and all others will report their greatest barriers to cessation (open ended), current motivation (1=very low; 10=very high), and readiness to quit. Follow-up surveys also will assess changes in unmet basic needs (items described in "Baseline") and problem resolution for each reason they called 2-1-1 at enrollment ("When you called 2-1-1 on <date> you asked for help with <problem>. Has that problem been resolved?"). Reactions to the quitline and navigation interventions and staff will be assessed with measures from our previous studies assessing usefulness (e.g., was it helpful?), satisfaction (would you recommend it to others?) user experience (were they easy to talk to?); quit coaches and navigators (similarity, liking, expertise, sincerity, trustworthiness); and intervention appropriateness (relevant to my life and situation, designed for someone like me).

All participants who complete the 6-month follow up survey (estimated N=1200) and report smoking abstinence and no use of nicotine replacement products in the past 7 days (estimated <14% = N<168) will be invited to biochemically assess carbon monoxide levels or cotinine levels. If participants are willing to participate, they will be mailed a urine test to measure their cotinine levels, which is a metabolite of nicotine. The urine test, which can be purchased at any local pharmacy over-the-counter, will be mailed to participants with instructions for sending the results. The study team will not receive any biological samples or testing materials in the mail. Instead, participants will be instructed to send a picture of their results to the study email account and/or phone account. The photo will include only the results: a photo of the dipstick next to the results card. No personal identifiable information will be included in the photo. The results will be linked to the participants study ID via their phone number from which the photo was sent. Consent will be obtained prior to sending the testing kit in the mail via phone script (see attached). Results will be recorded in participants study record. Incentives will be mailed to participants after result has been received by study team.

**1.14** Will participants be randomized?

Yes

**1.15** Will any of the following be used to collect information from the participant or others?

Screening questions or screening/eligibility questionnaires

Surveys

Questionnaires

Stimuli

Any other written assessments

Yes

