Using a 2x2 randomized factorial design, we will compare the effects of Standard and Specialized Quitlines with and without a Basic Needs navigator on smoking cessation among 2000 low-income smokers. The primary study outcome is self-reported 7-day point prevalence abstinence at 6-month follow up. All contacts with participants will be by telephone. This statewide field trial will recruit smokers who call United Way 2-1-1 Missouri. Smokers interested in quitting and joining our study will complete a phone survey and then be referred to the standard or specialized Missouri Tobacco Quitline, provided by Alere Wellbeing, Inc. Both 2-1-1 Missouri and Alere Wellbeing, Inc./Optum are research partners in this study. Embedding the study in these practice agencies will accelerate the path to application should our findings support it.

**1.4** Specify your research question(s), study aims or hypotheses:

Aim 1: Compare the relative and combined effects of Specialized Quitline services and Basic Needs navigation on use of the Missouri Tobacco Quitline by low-income smokers.

Primary research questions:

- What proportion of smokers in each study group enrolls in and receives Quitline services?
- Of those enrolled, does the number of counseling sessions completed vary by study group?
- Of those enrolled, does use of Quitline services (Print, Text2Stop, WebCoach) vary by study group?

Aim 2: Compare the relative and combined effects of Specialized Quitline services and Basic Needs navigation on quit attempts and abstinence among low-income smokers.

Primary research questions (again, by study group):

- What proportion report 7-day and 30-day point prevalence abstinence at 3 and 6 months?
- What proportion report quitting smoking for at least 24 hours (i.e., make a quit attempt)?
- What proportion report using any pharmacologic cessation aids, like nicotine replacement?

Aim 3: (Dissemination and Implementation Aim) Conduct scalability and economic evaluations to assess the sustainability of the study's referral and intervention approaches.

Primary research question (again, by study group):

A. What are the costs and benefits of each study condition per Quitline referral, per smoker interaction with the Quitline, and per successful quitter from the perspective of Quitline funders and providers?

**1.5** Background and significance and/or Preliminary studies related to this project:

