We will conduct analyses of secondary outcomes (7 and 30 day point prevalence abstinence, >24 hour quit attempt, use of pharmacotherapy, participation in cessation counseling) at 3 and 6 month follow up. Consistent with other reports in the literature, we also will compare the results from self-reported smoking cessation to results that adjust for biochemical validation. First, we will consider all participants who fail the biochemical validation and those that did not return a saliva sample to be smokers and recalculate abstinence rates by group. Second, we will recalculate abstinence rates by group, assuming that the true smoking cessation rate of participants who do not complete a follow up survey or do not return their saliva samples is the same rate as for those who did return a sample. Additionally, we will explore differences between people who do and do not agree to receive a kit and do and do not return a saliva sample. Analyses will be repeated with multiple logistic regression to include

potential baseline covariates (e.g., socio-demographics, rural/urban residence, nicotine dependence, readiness to quit). Cases with missing data on covariates will be excluded from analyses.

We also will conduct a series of sensitivity analyses to evaluate the robustness of our findings. To assess effects of protocol deviations, we will compare results of per-protocol analyses to ITT analysis. We will examine quit rate differences by intervention “dose” (i.e., number of completed quitline calls, number of navigator contacts), number of unmet basic needs, demographics, and smoking variables assessed at baseline, and extent of problem resolution at 3- and 6-month follow-up. We will assess the effect of missing data by comparing ITT results to a complete case (all data available at 6-month follow-up) analysis.

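### Quit-attempt, cessation-aid and counseling items look back to the previous survey, so the 6-month answers mix windows of about 3 and about 6 months

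*Protocol*

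**What the plan says.** Protocol 1.13 places surveys at 3 and 6 months after baseline. The quit-attempt item is filtered: only participants who report smoking in the past 7 days "will be asked if they quit for at least 24 hours since the previous survey". All participants report pharmacologic aids, "self-help, or counseling resources they have used since the prior survey". Neither item has a fixed number of months or an anchor date.

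The SAP (Aim 2) lists as secondary outcomes, besides abstinence, ">24 hour quit attempt, use of pharmacotherapy, participation in cessation counseling) at 3 and 6 month follow up". It does not define the period that each one covers.

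Protocol 1.4 lists quit attempts and pharmacologic aid use as two of the three Aim 2 research questions, also without a window. The documents do not say what someone who missed the 3-month survey is asked at 6 months, and they do not say that missing it ends follow-up.

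**The concern.** For someone who missed month 3, the previous survey is baseline. The 6-month answer then covers roughly twice the time that it covers for someone who answered at month 3. A longer window gives more chance of reporting at least one attempt or any aid use. The 6-month proportion is therefore a blend whose weights are set by survey completion.

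If completion is the same in every arm, the blend is hard to interpret but creates no spurious difference. If completion differs, part of the difference between arms comes from window length. Neither missing-data provision in the SAP deals with this. Counting unreachable participants as smokers, and comparing intention-to-treat with complete-case results, both concern absent answers. Here the answer is present but refers to a different period.

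**Working it through.** The plan has no figure to reproduce: it gives no 3-month response rate, quit-attempt rate or aid-use rate. What follows is an illustration.

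**Inputs from the documents.** 500 per arm and at least 60% reached at 6 months (SAP 1.23), so 500 × 0.60 = 300 respondents per arm, or 600 per side if two arms are pooled.

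**Assumed inputs.**
- q1, q2: probability of an attempt in months 0–3 and in months 3–6.
- r: share of 6-month respondents who also did the 3-month survey.

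**Formulas.** If attempts in the two periods are independent, the probability over 6 months is q6 = 1 − (1 − q1)(1 − q2). The observed 6-month proportion among respondents is r × q2 + (1 − r) × q6. The rejection rate is that of a two-sided pooled two-proportion z-test at 0.05.

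**Base case, no true effect.** With q1 = q2 = 0.40, q6 = 1 − 0.60 × 0.60 = 0.64.
- r = 0.85: 0.85 × 0.40 + 0.15 × 0.64 = 43.6%.
- r = 0.95: 0.95 × 0.40 + 0.05 × 0.64 = 41.2%.
- Spurious gap: 2.4 points, lower in the arm with better 3-month completion.

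**False-positive rate (nominal 5%).**

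| Assumptions | Gap (points) | 300 per arm | 600 per side |
|---|---|---|---|
| q = 0.40, r equal in both arms | 0 | 5% | 5% |
| q = 0.40, r = 85% vs 90% | 1.2 | 6.0% | 7.0% |
| q = 0.40, r = 85% vs 95% | 2.4 | 9.1% | 13.4% |
| Same, q6 rises half as much (52%) | 1.2 | 6.0% | 7.1% |
| q = 0.30, r = 85% vs 95% | 2.1 | 8.5% | 12.2% |
| q = 0.50, r = 85% vs 95% | 2.5 | 9.4% | 13.9% |
| q1 = 0.60, q2 = 0.30, r = 85% vs 95% | 4.2 | 19% | 33% |

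The last row has attempts concentrated early. That is plausible, because Protocol 1.13 describes a quit date within 30 days of enrollment and counseling spread over 1–3 months, but the rates are still assumed.

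**Direction when all randomized are counted.** Suppose non-responders are coded as making no attempt, and take the base-case rates.
- 6-month response 60% vs 63.5%: 0.60 × 43.6% = 26.2% and 0.635 × 41.2% = 26.2%. The distortion cancels.
- 6-month response 60% vs 70%: 26.2% and 0.70 × 41.2% = 28.8%. The sign reverses.

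**The case against.** Four points on the other side carry weight.

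1. **The premise has no figure behind it.** No document gives 3-month response or says that it differs by arm. The navigator duties in Protocol 1.13 do not include survey administration. Without a difference by arm there is no spurious difference between arms. This stands, and the effect on the comparison has to be stated conditionally. The mixed window itself does not depend on it.

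2. **The instruments are not shown.** Protocol 1.15 lists separate 3-month and 6-month surveys as attachments, and their wording may already fix a date. This also stands. If they do, one sentence in the SAP settles the matter.

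3. **The direction is not settled.** A reader might infer that the navigator arms, having more contact, would be made to look worse. That follows only in an analysis of respondents, and only if those arms complete the 3-month survey more often. The SAP's intention-to-treat rule includes everyone randomized but does not say how non-responders are coded for attempts or aid use. Coded as no attempt, better 6-month response pushes the other way, as shown above.

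4. **Analysts could fix it by derivation.** A reader might infer that the measure is flawed beyond repair at analysis. The documents do not support that. Among 6-month respondents, those who missed month 3 already report back to baseline, and those who did both surveys supply two adjoining windows. What is missing is a stated rule.

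On size, 13% applies to a pooled navigator-versus-none contrast. The Aim 2 model that the SAP states compares each group with standard quitline and no navigator, so about 9% at 300 per arm is the closer figure.

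**Conclusion.** The point holds as a modest gap in outcome definition. On a plain reading of Protocol 1.13, the 6-month figures for quit attempts, cessation aids and counseling mix two recall windows, and nothing in the SAP separates or aligns them.

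The distortion of the group comparison is conditional. It needs 3-month completion among 6-month respondents to differ by arm. Under the assumed base case it is 2.4 points, with about 9% false positives at 300 per arm. It falls to about 6% with a 5-point completion gap or correlated attempts, and rises if attempts cluster early. The documents do not establish its direction.

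It would be wrong to read this as a threat to the trial's main result. The primary outcome, 7-day abstinence at 6 months, and 30-day abstinence have fixed windows, and the 3-month results have baseline as their previous survey. The affected outcomes are secondary in the SAP, although two of them answer Aim 2 questions in Protocol 1.4.

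**What to change.** - **Define one window.** Make the 6-month outcome any 24-hour quit attempt from baseline to 6 months among 6-month respondents, with parallel outcomes for any aid use and any counseling use. Combine both surveys for those who did both. Use wording anchored to enrollment for those who missed month 3.
- **Count abstainers.** Treat 7-day abstinence at either survey as an attempt, because the item goes only to those who smoked in the past 7 days.
- **Report completion.** Give 3-month survey completion by arm among 6-month respondents.
- **Keep the all-randomized version as a sensitivity analysis.** Counting missing as no attempt makes the result depend on response. It also does not give everyone the same window: someone who answered only at month 3 contributes 3 months, and someone who answered neither survey contributes none.

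The cost is small: a derived-variable definition and, if the 6-month survey lacks an anchor date, one wording change. The downside is that the main 6-month figure no longer isolates months 3–6. That figure can be reported separately for participants who did both surveys.
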